ANNEX 3. Attention and memory test: TMT

Trail Making Test (TMT) Parts A & B

Instructions:

Both parts of the Trail Making Test consist of 25 circles distributed over a sheet of paper. In Part A, the circles are numbered 1 - 25, and the patient should draw lines to connect the numbers in ascending order. In Part B, the circles include both numbers (1 - 13) and letters (A - L); as in Part A, the patient draws lines to connect the circles in an ascending pattern, but with the added task of alternating between the numbers and letters (i.e., 1-A-2-B-3-C, etc.). The patient should be instructed to connect the circles as quickly as possible, without lifting the pen or pencil from the paper. Time the patient as he or she connects the "trail." If the patient makes an error, point it out immediately and allow the patient to correct it. Errors affect the patient's score only in that the correction of errors is included in the completion time for the task. It is unnecessary to continue the test if the patient has not completed both parts after five minutes have elapsed.

Step 1: Give the patient a copy of the Trail Making Test Part A worksheet and a pen or pencil.

Step 2: Demonstrate the test to the patient using the sample sheet (Trail Making Part A – SAMPLE).

Step 3: Time the patient as he or she follows the "trail" made by the numbers on the test. Step 4: Record the time.

Step 5: Repeat the procedure for Trail Making Test Part B.

Scoring:

Results for both TMT A and B are reported as the number of seconds required to complete the task; therefore, higher scores reveal greater impairment.

Average Deficient Rule of Thumb Trail A 29 seconds > 78 seconds Most in 90 seconds Trail B

75 seconds > 273 seconds Most in 3 minutes

Sources:

- Reitan RM. Validity of the Trail Making test as an indicator of organic brain damage. *Percept Mot Skills*. 1958;8:271-276.

Trail Making Test Part A

Patient's Name: Date:

Trail Making Test Part A – SAMPLE

Trail Making Test Part B

Patient's Name: Date:

Trail Making Test Part B – SAMPLE

Institut Català de la Salut

ANNEX 4. Attention and memory test: SDMT

Institut Català de la Salut

ANEXO 5. Montreal Cognitive Assessment (MoCA)

ANEXO 6. Mini-Mental State Examination (MMSE)

Mini-Mental State Examination (MMSE)

Patient's code:

Date:

Instructions: Ask the questions in the order listed. Score one point for each correct response within each question or activity.

Maximum Score	Patient's Score	Questions
5		"What is the year? Season? Date? Day of the week? Month?"
5		"Where are we now: State? County? Town/city? Hospital? Floor?"
3		The examiner names three unrelated objects clearly and slowly, then asks the patient to name all three of them. The patient's response is used for scoring. The examiner repeats them until patient learns all of them, if possible. Number of trials:
5		"I would like you to count backward from 100 by sevens." (93, 86, 79, 72, 65, …) Stop after five answers. Alternative: "Spell WORLD backwards." (D-L-R-O-W)
3		"Earlier I told you the names of three things. Can you tell me what those were?"
2		Show the patient two simple objects, such as a wristwatch and a pencil, and ask the patient to name them.
1		"Repeat the phrase: 'No ifs, ands, or buts.'"
3		"Take the paper in your right hand, fold it in half, and put it on the floor." (The examiner gives the patient a piece of blank paper.)
1		"Please read this and do what it says." (Written instruction is "Close your eyes.")
1		"Make up and write a sentence about anything." (This sentence must contain a noun and a verb.)
1		"Please copy this picture." (The examiner gives the patient a blank piece of paper and asks him/her to draw the symbol below. All 10 angles must be present and two must intersect.)
30		TOTAL

1

(Adapted from Rovner & Folstein, 1987)

Source: www.medicine.uiowa.edu/igec/tools/cognitive/MMSE.pdf Provided by NHCQF, 0106-410 Instructions for administration and scoring of the MMSE

Orientation (10 points):

- Ask for the date. Then specifically ask for parts omitted (e.g., "Can you also tell me what season it is?"). One point for each correct answer.
- Ask in turn, "Can you tell me the name of this hospital (town, county, etc.)?" One point for each correct answer.

Registration (3 points):

- Say the names of three unrelated objects clearly and slowly, allowing approximately one second for each. After you have said all three, ask the patient to repeat them. The number of objects the patient names correctly upon the first repetition determines the score (0-3). If the patient does not repeat all three objects the first time, continue saying the names until the patient is able to repeat all three items, up to six trials. Record the number of trials it takes for the patient to learn the words. If the patient does not eventually learn all three, recall cannot be meaningfully tested.
- After completing this task, tell the patient, "Try to remember the words, as I will ask for them in a little while."

Attention and Calculation (5 points):

- Ask the patient to begin with 100 and count backward by sevens. Stop after five subtractions (93, 86, 79, 72, 65). Score the total number of correct answers.
- If the patient cannot or will not perform the subtraction task, ask the patient to spell the word "world" backwards. The score is the number of letters in correct order (e.g., dlrow=5, dlorw=3).

Recall (3 points):

• Ask the patient if he or she can recall the three words you previously asked him or her to remember. Score the total number of correct answers (0-3).

Language and Praxis (9 points):

- Naming: Show the patient a wrist watch and ask the patient what it is. Repeat with a pencil. Score one point for each correct naming (0-2).
- Repetition: Ask the patient to repeat the sentence after you ("No ifs, ands, or buts."). Allow only one trial. Score 0 or 1.
- 3-Stage Command: Give the patient a piece of blank paper and say, "Take this paper in your right hand, fold it in half, and put it on the floor." Score one point for each part of the command correctly executed.
- Reading: On a blank piece of paper print the sentence, "Close your eyes," in letters large enough for the patient to see clearly. Ask the patient to read the sentence and do what it says. Score one point only if the patient actually closes his or her eyes. This is not a test of memory, so you may prompt the patient to "do what it says" after the patient reads the sentence.

- Writing: Give the patient a blank piece of paper and ask him or her to write a sentence for you. Do not dictate a sentence; it should be written spontaneously. The sentence must contain a subject and a verb and make sense. Correct grammar and punctuation are not necessary.
- Copying: Show the patient the picture of two intersecting pentagons and ask the patient to copy the figure exactly as it is. All ten angles must be present and two must intersect to score one point. Ignore tremor and rotation.

(Folstein, Folstein & McHugh, 1975)

2

Source: www.medicine.uiowa.edu/igec/tools/cognitive/MMSE.pdf Provided by NHCQF, 0106-410 Interpretation of the MMSE

Method	Score	Interpretation
Single Cutoff	<24	Abnormal
Range	<21	Increased odds of dementia
	>25	Decreased odds of dementia
Education	21	Abnormal for 8 th grade education
	<23	Abnormal for high school education
	<24	Abnormal for college education
Severity	24-30	No cognitive impairment
	18-23	Mild cognitive impairment
	0-17	Severe cognitive impairment

Sources:

Source: www.medicine.uiowa.edu/igec/tools/cognitive/MMSE.pdf Provided by NHCQF, 0106-410

ANNEX 7. System Usability Scale (SUS) for patients

System Usability Scale (SUS) for patients					
Simulation assessment - System usability scale	Strongly disagree	little disagree	Neutral	little agree	l quite agree
1 I think I would like to use this program frequently					
2 I think the program is too complex					
3 I think that exercises with glasses are more entertaining than in a conventional way					
4 I think the simulation options are clear and well integrated 5 I think some options are difficult to follow					
6 I think people will be able to learn how to use this system easily					
7 I felt comfortable using this system					
8 I had to learn many things before I could use the system					
VR headset rating - Quest 2	Strongly disagree	little disagree	Neutral	little agree	l quite agree
1 The glasses were very heavy and uncomfortable					
2 The use of glasses and controls has been very complicated					
3 I have felt tiredness in my arms and fingers					
4 I have felt visual discomfort					
5 I have felt dizzy					
6 I have felt a headache					
7 I had to stop the simulation due to the aforementioned discomfort					
8 I think it would be comfortable to wear these glasses for a long time					

COMMENTS:

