5.2 Design

This study will be prospective and non-randomized in design. Patients will be selected from among those who already attend cognitive rehabilitation sessions at the CSSC Day Hospital. There will be no control group in this pilot study, as the primary objective is to evaluate the usability and acceptability of the intervention.

Experimental group: This group will be made up of 20 patients who attend cognitive rehabilitation sessions at the CSSC Day Hospital. These patients will participate in 8 cognitive rehabilitation sessions that will incorporate the VR experiences developed for this study.

Intervention

Sessions:

The 8 sessions will be held two days a week, at the time when the included participants have an appointment for the conventional cognitive rehabilitation program at the CSSC Day Hospital.

Equipment and Technology:

We use Oculus Quest 2 glasses and their hand tracking technology, which allows for a more immersive and less complicated experience for participants, especially those with MCI.

Developed Virtual Reality Experiences:

A) Interactive Cognitive Stimulation Exercises (Declarative Memory, Executive Functions):

Developed jointly by the BSA VR and Reality Telling teams, following the researchers' guidelines, three types of sequential interactive exercises have been created:

Step 1- Make a Purchase at the Supermarket:

- Scenario: Virtual supermarket.
- Avatar: An animated avatar greets the participant and provides instructions.
- Objective: Select ingredients to make a potato omelet or gazpacho.
- Interaction: Participants use hand tracking technology to grab products and place them in a virtual cart.
- Feedback: A success or error audio is emitted based on the product selection.

Step 2- Pay for the Purchase:

- Scenario: Checkout area of the virtual supermarket.
- Avatar: An animated avatar greets the participant and provides instructions.
- Objective: Pay the exact amount for the selected products.
- Interaction: Select 3D models of bills and coins to reach the correct sum.
- Feedback: An avatar and audio provide confirmation or correction.

Step 3- Sort the Recipe Steps:

- Scenario: Virtual kitchen.
- Avatar: An animated avatar greets the participant and provides instructions.
- Objective: Sort photos of the recipe steps.
- Interaction: Drag and drop photos into a numbered panel.
- Feedback: Confirmation of the avatar.

Scenario details:

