5.4.2 Other variables

- Age
- Sex
- Etiology of cognitive impairment
- Schooling
- Exposure to other treatments: Any additional medication or cognitive therapy that the patient is simultaneously participating in will be recorded.

5.5 Study Evaluations:

Visit	Procedures		
Selection visit (Pre-study)	Informed consent, collection of demographic data and results of cognitive function variables		
Visit 1 (Session 1)	Starting VR training sessions		
Visit 2 (Session 8 - Final)	Completion of the VR training sessions, questionnaires on cognitive function and satisfaction and usability variables.		

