5.6 Sample size

The sample size for this pilot study has been established at 20 patients. This decision is based on several factors:

Preliminary nature of the study: As this is a pilot study, the primary objective is to evaluate the usability and acceptability of the virtual reality intervention, rather than to demonstrate effectiveness. Pilot studies typically have smaller sample sizes than full studies.

Resources and capacity: The capacity of the El Carme Socio-Health Center in Badalona and the available resources (both in terms of staff and virtual reality equipment) also influence the sample size. Ensuring that each participant can receive appropriate care and support is

critical to accurate data collection and a positive patient experience.

Patient variability: Although the sample size is small, it is expected to reflect the diversity of the patient population in terms of severity of cognitive impairment, gender, age, etc. This diversity may provide a deeper understanding of how different types of patients may interact with virtual reality technology.

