8. MANAGEMENT AND COMMUNICATION OF ADVERSE REACTIONS

As this study uses virtual reality in cognitive stimulation for patients with cognitive impairment and does not involve the use of medications, the management and communication of adverse drug reactions is not applicable in this context.

However, any adverse side effects associated with the use of virtual reality technology, such as dizziness, nausea or disorientation, will be carefully recorded and monitored by the research team. Healthcare professionals are trained to handle these incidents and will provide necessary care to study participants should these adverse effects occur.

The research team agrees to inform the collaborating company, Reality Telling, about any incident that occurs during the study, respecting the confidentiality of the participants. In the event of a serious adverse reaction, the research team will take necessary steps to ensure the safety of the participant and determine whether their participation in the study needs to be adjusted or discontinued.

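### Annex 7 records VR symptoms and stopping on an agreement scale, with no reference period and no pre-VR reading, so existing complaints cannot be cleanly separated from VR effects and any patient count rests on a cut chosen afterwards

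*Combined protocol and SAP*

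**What the plan says.** Annex 7 is the patient questionnaire. Its second block, the headset rating, has eight statements on a five-step scale from disagreement to agreement with a neutral midpoint. Items 3 to 6 are symptoms: arm and finger tiredness, "I have felt visual discomfort", "I have felt dizzy" and "I have felt a headache". Item 7 is an event: "I had to stop the simulation due to the aforementioned discomfort".

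The other relevant parts of the plan are:

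- **Before VR.** The selection visit in section 5.5 lists "Informed consent, collection of demographic data and results of cognitive function variables". No symptom question appears.
- **Comparator.** Section 5.2: "There will be no control group in this pilot study".
- **Size.** Section 5.6: "The sample size for this pilot study has been established at 20 patients".
- **Timing.** Section 5.4.1 has the patient questionnaires given after the eighth session, and the section 5.5 table agrees. Section 6.1 has them completed after every session.
- **Analysis.** Section 5.7 describes the usability scores. It has no rule for the symptom items and no symptom table.
- **Separate record.** Section 8 says that "any adverse side effects associated with the use of virtual reality technology, such as dizziness, nausea or disorientation, will be carefully recorded", with study staff responsible for keeping watch. It names no form, case definition, grading or schedule.

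**The concern.** A symptom either occurred or did not, and it had some severity. An agreement scale captures neither directly. A neutral answer to having felt dizzy could mean no, slightly, or not sure. A neutral answer to having had to stop has no meaning as an event.

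Participants are 60 or older and can have headache, dizziness or tired arms without VR. With no control group, a reading before first headset use is the simplest internal reference for patient-reported tolerability, and the plan does not take one.

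What is at stake is the tolerability message of the pilot. Section 7.1 lists dizziness and disorientation as the first risk, and section 5.8 says the findings will inform later research. Annex 7 is the only structured form in the plan on which patients report these symptoms. If its answers are ambiguous and have no reference point, the pilot cannot say with any precision how many patients VR made unwell.

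**Working it through.** The plan states no symptom rate, so there is no figure of its own to reproduce. The calculations below show how large the two problems could be.

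**Inputs.** From the documents: n = 20 (section 5.6), one group (section 5.2), and 8 sessions at two a week, so 8 / 2 = 4 weeks (section 5.2). Assumed, because the documents give nothing: the share b of patients who would report a given symptom without VR, taken as 10% to 30%; a true VR effect v of 0 or 10%; and an invented set of answers for the scale example.

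**1. Background complaints.** The expected number reporting with no VR effect is 20 × b. The chance of at least one is 1 − (1 − b)^20. If background and VR complaints are independent, the observed share is 1 − (1 − b)(1 − v).

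| b (assumed) | Expected of 20, v = 0 | Chance of at least one, v = 0 | Observed share, v = 10% |
|---|---|---|---|
| 10% | 2 | 88% | 1 − 0.9 × 0.9 = 19% |
| 20% | 4 | 99% | 1 − 0.8 × 0.9 = 28% |
| 30% | 6 | 99.9% | 1 − 0.7 × 0.9 = 37% |

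**2. Choice of cut.** Suppose the 20 dizziness answers were 14 on the disagree side, 2 neutral, 3 on the weaker agree box and 1 on the stronger. Exact (Clopper-Pearson) 95% intervals:

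| Counted as affected | Patients | Share | 95% interval |
|---|---|---|---|
| Stronger agree only | 1/20 | 5% | 0.1% to 24.9% |
| Either agree box | 3 + 1 = 4/20 | 20% | 5.7% to 43.7% |
| Neutral or above | 2 + 3 + 1 = 6/20 | 30% | 11.9% to 54.3% |

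The same answers give 5%, 20% or 30%.

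**3. Questionnaire timing.** If the form is completed after each session, the relevant background is the chance per session, which may be much lower than over four weeks. It still accumulates. With per-session background s, independent across sessions, the chance of at least one report in 8 is 1 − (1 − s)^8. That is 7.7% for s = 1%, 33.7% for s = 5% and 57.0% for s = 10%. The conflict between sections 5.4.1 and 6.1 therefore decides both the recall window and the background that applies.

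**The case against.** A reader might infer that no count of affected patients can be obtained at all. The documents do not support that. The scale can be cut, as the example above does, and the section 8 record could give a count independent of Annex 7. Its three named effects are examples, so headache or visual discomfort are not ruled out. What is missing is a rule set in advance.

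A reader might also infer that the plan treats every complaint as caused by VR. It does not say so. The items stand under a headset heading, item 7 ties the discomfort to the simulation, and section 8 covers effects linked to VR. Many patients would read the dizziness item as dizziness with the headset on. Misattribution is a risk, not a stated rule.

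Other points on that side also carry weight. Section 7.1 has patients closely supervised, and onset seen during a session is evidence of cause. Section 5.3 excludes high sensitivity to motion sickness and uncorrectable blurred vision, which should lower the background for dizziness and visual discomfort. No symptom rate is a listed outcome, and showing all five answer categories would need no cut.

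These points narrow the concern but do not remove it. The heading supplies context, not a reference period or a comparison with the usual state. Staff attribution under section 8 has no form, grading or earlier reading to work from. A table of all five categories would still leave the neutral answers, and item 7, without a clear meaning.

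**Conclusion.** The point holds as a weakness of measurement. Followed as written, Annex 7 gives symptom answers that are ambiguous in format and have no pre-VR reference, in a study with no control group. Existing complaints cannot be cleanly separated from VR effects, and any headline count would rest on a cut chosen after the answers are seen. The section 8 record is a partial second source.

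The size is illustrative. The 2 to 6 of 20 and the 19% to 37% rest on an assumed 10% to 30% background, and the latter also on independence of background and VR complaints. The spread from 5% to 30% rests on an invented set of answers. If patients read the items strictly as headset experience, the background, and so the distortion, would be smaller.

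The primary usability description is not invalidated. This is a worthwhile and inexpensive improvement to a pilot whose tolerability findings are meant to be used later.

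**What to change.** 1. Take headset items 3 to 7 off the agreement scale. Ask items 3 to 6 as none, mild, moderate or severe, with a stated reference period such as during or just after the headset sessions.
2. Ask the same four symptoms once, as current state on the same severity scale, before the first headset use.
3. Ask item 7 as yes or no, with the number of sessions stopped.
4. State in section 5.7 that the report will give, for each symptom, the number of patients out of those treated whose rating is new or worse than before VR, and the number who stopped. Show these beside the section 8 record, and say on what form and with what grading that record is kept.
5. Reconcile section 5.4.1 with section 6.1 on whether the questionnaire is completed once or after each session, and match the reference period to the answer.

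The cost is five reworded items and four short questions asked once before session 1, with no added visit. One limit should be stated in the report: a single pre-VR rating deals well with persistent complaints but only partly with fluctuating ones such as headache, so some patients counted as new or worse may still reflect background.

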ANNEX 8. System Usability Scale (SUS) for professionals

System Usability Scale (SUS) for professionals					
Simulation assessment - System usability scale	Strongly disagree	little disagree	Neutral	little agree	l quite agree
1 I believe this program will help improve the quality of patient care.					
2 I think the program interface is intuitive for the user.					
3 I believe that the program can be easily integrated into daily care practice.					
4 I believe that the functions and features of simulation are clear and relevant to patient care.	Strongly disagree	little disagree	Neutral	little agree	l quite agree
5 Some of the functionality of this system may be difficult for patients to understand or use.					
6 I believe that patients will be able to learn to use this system easily.					
7 I have felt comfortable using this system for patient care.					
8 I have needed additional time to learn how to use this system correctly.					
VR headset rating - Quest 2					
1 I think the weight and design of the glasses couldbe uncomfortable for patients.					
2 I think that the use of glasses and controls could be complicated for some patients.					
3 I think patients would be able to wear these glasses for an extended period of time without discomfort.					

COMMENTS:
